9. PROTECTION OF HUMAN SUBJECTS

The survey is non-interventional and totally anonymous to the study sponsor. Data collected will remain absolutely confidential and only aggregated data will be analysed and communicated in a report.

9.1 COMPLIANCE WITH LAWS AND REGULATIONS

This study will be conducted in full conformance with the Guidelines for Good Pharmacoepidemiological Practice published by the International Society of Pharmacoepidemiology and the laws and regulations of the country in which the research is conducted.

The study will comply with national and European Union requirements for ensuring the well-being and rights of participants in non-interventional post-authorization safety studies.

9.1.1 Informed Consent

HCPs participating in the study have to consent for data collection and need to be informed about the purpose of the survey and their storage of data. will ensure that the national and European data protection and ethical requirements are met for the HCPs. This will be done electronically.

9.1.2 Institutional Review Board or Ethics Committee

Each participating country should locally ensure all necessary regulatory submissions (e.g., IRB/Independent Ethics Committee) are performed in accordance with local regulations including local data protection regulations.

9.1.3 Financial Disclosure

HCPs will be offered a compensation for the time spent participating in this survey (that they may refuse). For HCPs involved in the HCP survey, the estimated time to complete the questionnaire is 15 minutes. The amount of this compensation will be determined according to the EphMRA recommendations and the Association of Opinion and Behaviour in health field research companies (ASOCS) charter, which states:

"When it is necessary to compensate a physician in return to the time spent during an interview or a group meeting, the compensation must not exceed the fees commonly taken by the physician for his/her advice or consultation and must be proportional to the

Alecensa—F. Hoffmann-La Roche Ltd Protocol BO40643, Version 1

time provided. The compensations should be clearly stated prior to the physician's participation in the survey. They must be declared to the tax authorities in accordance with applicable laws."

10. MANAGEMENT AND REPORTING OF ADVERSE EVENTS/ ADVERSE REACTIONS

This study is a survey to evaluate the effectiveness of material implemented as RMM. This survey does not involve data collection on clinical endpoints on individual patients. Although adverse event information is not being actively solicited via this protocol, any safety information for an individual patient that is volunteered by a study physician during the course of this research must be reported as described below.

In the event that a study participant reports a safety event associated with a Roche product, will forward any information on adverse events (AE; serious and non-serious) that involve Roche products to the Roche Pharmacovigilance department using the AE report form available via the national spontaneous reporting system. This will be done within the timeline of 24h for serious AE or within 30 days for non-serious AE.

11. PUBLICATION OF DATA AND PROTECTION OF TRADE SECRETS

Regardless of the outcome of a study, Roche is dedicated to openly providing information on the study to HCPs and to the public, both at scientific congresses and in peer-reviewed journals. The marketing authorization holder will comply with all requirements for publication of study results.

Appendix 1- ENCePP Checklist

Doc.Ref. EMA/540136/2009

ENCePP Checklist for Study Protocols (Revision 3)

Adopted by the ENCePP Steering Group on 01/07/2016

The European Network of Centres for Pharmacoepidemiology and Pharmacovigilance (ENCePP) welcomes innovative designs and new methods of research. This Checklist has been developed by ENCePP to stimulate consideration of important principles when designing and writing a pharmacoepidemiological or pharmacovigilance study protocol. The Checklist is intended to promote the quality of such studies, not their uniformity. The user is also referred to the ENCePP Guide on Methodological Standards in Pharmacoepidemiology, which reviews and gives direct electronic access to guidance for research in pharmacoepidemiology and pharmacovigilance.

For each question of the Checklist, the investigator should indicate whether or not it has been addressed in the study protocol. If the answer is "Yes", the section number of the protocol where this issue has been discussed should be specified. It is possible that some questions do not apply to a particular study (for example, in the case of an innovative study design). In this case, the answer 'N/A' (Not Applicable) can be checked and the "Comments" field included for each section should be used to explain why. The "Comments" field can also be used to elaborate on a "No" answer.

This Checklist should be included as an Annex by marketing authorisation holders when submitting the protocol of a non-interventional post-authorisation safety study (PASS) to a regulatory authority (see the Guidance on the format and content of the protocol of non-interventional post-authorisation safety studies). The Checklist is a supporting document and does not replace the format of the protocol for PASS as recommended in the Guidance and Module VIII of the Good pharmacovigilance practices (GVP).

Study title:

ALECENSA SURVEY TO PRESCRIBERS: EFFECTIVENESS MEASURE TO INVESTIGATE THE CORRECT IMPLEMENTATION OF ALECTINIB LABEL GUIDANCE BY PRESCRIBERS

Study reference number: BO40643

Sect	tion 1: Milestones	Yes	Νο	N/A	Section Number
1.1	Does the protocol specify timelines for				
	1.1.1 Start of data collection ²	\square			3 and 5
	1.1.2 End of data collection ³	\square			3 and 5

² Date from which information on the first study is first recorded in the study dataset or, in the case of secondary use of data, the date from which data extraction starts.

³ Date from which the analytical dataset is completely available.

Section 1: Milestones	Yes	No	N/A	Section Number
1.1.3 Study progress report(s)			\boxtimes	
1.1.4 Interim progress report(s)			\square	
1.1.5 Registration in the EU PAS register	\boxtimes			5
1.1.6 Final report of study results.	\square			3 and 5

Comments:

Sect	ion 2: Research question	Yes	No	N/ A	Section Number
2.1	Does the formulation of the research question and objectives clearly explain:	\square			
	2.1.1 Why the study is conducted? (e.g. to address an important public health concern, a risk identified in the risk management plan, an emerging safety issue)	\boxtimes			3, 6.1, 7.1, and 8.1.1
	2.1.2 The objective(s) of the study?	\boxtimes			3 and 7.2
	2.1.3 The target population? (i.e. population or subgroup to whom the study results are intended to be generalised)	\boxtimes			3 and 8.2.2
	2.1.4 Which hypothesis(-es) is (are) to be tested?			\boxtimes	
	2.1.5 If applicable, that there is no a priori hypothesis?			\boxtimes	

Comments:

Sect	ion 3: Study design	Yes	No	N/ A	Section Number
3.1	Is the study design described? (e.g. cohort, case- control, cross-sectional, new or alternative design)	\square			3 and 8.1
3.2	Does the protocol specify whether the study is based on primary, secondary or combined data collection?	\boxtimes			3 and 8.4
3.3	Does the protocol specify measures of occurrence? (e.g. incidence rate, absolute risk)			\boxtimes	
3.4	Does the protocol specify measure(s) of association? (e.g. relative risk, odds ratio, excess risk, incidence rate ratio, hazard ratio, number needed to harm (NNH) per year)			\boxtimes	
3.5	Does the protocol describe the approach for the collection and reporting of adverse events/adverse reactions? (e.g. adverse events that will not be collected in case of primary data collection)				10

Sec	tion 4: Source and study populations	Yes	No	N/ A	Section Number
4.1	Is the source population described?	\square			3 and 8.2
4.2	Is the planned study population defined in terms of:				
	4.2.1 Study time period?	\square			3
	4.2.2 Age and sex?			\square	
	4.2.3 Country of origin?	\square			8.2
	4.2.4 Disease/indication?			\square	8.2
	4.2.5 Duration of follow-up?			\square	
4.3	Does the protocol define how the study population will be sampled from the source population? (e.g. event or inclusion/exclusion criteria)				8.2

Comments:

	tion 5: Exposure definition and Isurement	Yes	Νο	N/ A	Section Number
5.1	Does the protocol describe how the study exposure is defined and measured? (e.g. operational details for defining and categorising exposure, measurement of dose and duration of drug exposure)				
5.2	Does the protocol address the validity of the exposure measurement? (e.g. precision, accuracy, use of validation sub-study)				
5.3	Is exposure classified according to time windows? (e.g. current user, former user, non-use)				
5.4	Is exposure classified based on biological mechanism of action and taking into account the pharmacokinetics and pharmacodynamics of the drug?				
Com	ments:				

	ion 6: Outcome definition and surement	Yes	No	N/ A	Section Number
6.1	Does the protocol specify the primary and secondary (if applicable) outcome(s) to be investigated?				3 and 7.2
6.2	Does the protocol describe how the outcomes are defined and measured?	\square			3 and 8.7
6.3	Does the protocol address the validity of outcome measurement? (e.g. precision, accuracy, sensitivity, specificity, positive predictive value, prospective or retrospective ascertainment, use of validation sub-study)				
6.4	Does the protocol describe specific endpoints relevant for Health Technology Assessment? (e.g. HRQoL, QALYS, DALYS, health care services utilisation, burden of disease, disease management)				

Comments:

Sect	ion 7: Bias	Yes	No	N/ A	Section Number
7.1	Does the protocol describe how confounding will be addressed in the study?			\boxtimes	
	7.1.1. Does the protocol address confounding by indication if applicable?			\boxtimes	
7.2	Does the protocol address:				
	7.2.1. Selection biases (e.g. healthy user bias)				8.9
	7.2.2. Information biases (e.g. misclassification of exposure and endpoints, time-related bias)	\square			8.9
7.3	Does the protocol address the validity of the study covariates?				

Comments:

Section 8: Effect modification		Yes	Νο	N/ A	Section Number
8.1	Does the protocol address effect modifiers? (e.g. collection of data on known effect modifiers, sub- group analyses, anticipated direction of effect)		\boxtimes		

Comments:

Sect	ion 9: Data sources	Yes	No	N/ A	Section Number
9.1	Does the protocol describe the data source(s) used in the study for the ascertainment of:				
	9.1.1 Exposure? (e.g. pharmacy dispensing, general practice prescribing, claims data, self-report, face-to-face interview)			\boxtimes	
	9.1.2 Outcomes? (e.g. clinical records, laboratory markers or values, claims data, self-report, patient interview including scales and questionnaires, vital statistics)				3 and 8.4.2
	9.1.3 Covariates?			\square	
9.2	Does the protocol describe the information available from the data source(s) on:				
	9.2.1 Exposure? (e.g. date of dispensing, drug quantity, dose, number of days of supply prescription, daily dosage, prescriber)			\boxtimes	
	9.2.2 Outcomes? (e.g. date of occurrence, multiple event, severity measures related to event)			\boxtimes	
	9.2.3 Covariates? (e.g. age, sex, clinical and drug use history, co-morbidity, co-medications, lifestyle)			\boxtimes	
9.3	Is a coding system described for:				
	9.3.1 Exposure? (e.g. WHO Drug Dictionary, Anatomical Therapeutic Chemical (ATC) Classification System)			\boxtimes	
	9.3.2 Outcomes? (e.g. International Classification of Diseases (ICD)-10, Medical Dictionary for Regulatory Activities (MedDRA))			\boxtimes	
	9.3.3 Covariates?				
9.4	Is a linkage method between data sources described? (e.g. based on a unique identifier or other)			\square	

Comments:

Section 10: Analysis plan		No	N/ A	Section Number
10.1 Is the choice of statistical techniques described?	\boxtimes			3 and 8.7
10.2 Are descriptive analyses included?	\square			3 and 8.7
10.3 Are stratified analyses included?	\square			3 and 8.7
10.4 Does the plan describe methods for adjusting for confounding?			\boxtimes	
10.5 Does the plan describe methods for handling missing data?	\boxtimes			8.7
10.6 Is sample size and/or statistical power estimated?				8.5.1

Section 11: Data management and quality control		No	N/ A	Section Number
11.1 Does the protocol provide information on data storage? (e.g. software and IT environment, database maintenance and anti-fraud protection, archiving)	\boxtimes			8.8.4
11.2 Are methods of quality assurance described?	\square			8.6.1
11.3 Is there a system in place for independent review of study results?				8.8.1

Comments:

Section 12: Limitations		Yes	No	N/ A	Section Number
12.1 Does the study res	protocol discuss the impact on the ults of:				
12.1.1 Se	lection bias?	\boxtimes			8.9
12.1.2 Int	formation bias?	\boxtimes			8.9
(e.g. ant biases, v	sidual/unmeasured confounding? icipated direction and magnitude of such alidation sub-study, use of validation and data, analytical methods)				
(e.g. study	protocol discuss study feasibility? size, anticipated exposure, duration of follow- rt study, patient recruitment)	\boxtimes			8.5.2

Comments:

Section 13: Ethical issues		No	N/ A	Section Number
13.1 Have requirements of Ethics Committee/ Institutional Review Board been described?	\square			9.3
13.2 Has any outcome of an ethical review procedure been addressed?		\boxtimes		
13.3 Have data protection requirements been described?				8.8.4

Comments:

Section 14: Amendments and deviations	Yes	No	N/ A	Section Number
14.1 Does the protocol include a section to document amendments and deviations?	\square			4

Comments:

Section 15: Plans for communication of study results	Yes	No	N/ A	Section Number
15.1 Are plans described for communicating study results (e.g. to regulatory authorities)?	\boxtimes			11
15.2 Are plans described for disseminating study results externally, including publication?				11

Comments:

Name of the main author of the protocol: _____

Date: / /

Signature: _____

This survey is a non-interventional post-authorization safety study that has been designed in order to comply with Article 21a.(b) of Directive 2001/83/EC and evaluate the effectiveness of risk minimization measures for Alecensa® (alectinib) in the EU. In particular, to assess physicians' awareness and knowledge of important identified risks (warnings and precautions) and specific clinical measures to address them as described in the Summary of Product Characteristics (SPC).

The survey has been agreed with the European Medicines Agency (EMA) and it is sponsored by F.Hoffmann-La Roche (Roche), the Marketing Authorisation Holder (MAH) of Alecensa®.

, is in charge of the implementation of this survey and the analysis of the results on Roche's behalf.

Your identity will always remain confidential. The results obtained from the survey will be disclosed in aggregated form to Roche and regulatory agencies, thus protecting your identity.

We greatly appreciate your participation in this research survey.

The questionnaire will take approximately 15 minutes to complete.

As appreciation for the time you will dedicate to complete the questionnaire you will be compensated with *[to be adapted to the specialty and country]*.

[figure not shown]

[figure not shown]

[figure not shown]

[figure not shown]

Alecensa—F. Hoffmann-La Roche Ltd Protocol BO40643, Version 1

Alecensa—F. Hoffmann-La Roche Ltd Protocol BO40643, Version 1

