8.4.2 Data Collection

Questionnaire

The questionnaire will include multiple-choice, open, and closed questions as appropriate and will be sent to the participating HCPs to collect information on their awareness, knowledge, and clinical practice about the specific guidance included in the label to minimize the risk of ILD/pneumonitis, hepatotoxicity, photosensitivity, bradycardia, severe myalgia, and CPK elevations.

The questionnaire will be translated into the relevant local languages. Translation will be done using the back and forth method of translation (i.e., from English into local language and then from local language into English). Physicians selected randomly from a panel of active physicians (i.e., physicians who regularly complete questionnaires of this nature) of the relevant specialities in the **second** database will ensure the meaning of the questions is retained in the translations (2-3 physicians per country). Before deployment, the questionnaire will be field tested to ensure accuracy.

The HCP questionnaire completion is estimated to take about 15 minutes.

Conduct of survey

For data collection a period of up to 6 months is planned. Data collection will be conducted between 18 and 24 months after the first line treatment approval by the European Medicines Agency (EMEA). In this 6-month time frame the fieldwork start date may vary by country based on the date of local market launch.

To ensure comprehension of the invitation and the survey, the entire HCP outreach will be conducted in the respective country's local language. The survey and invitation as well as any reminders will be translated by native speakers of the respective language at

HCPs will be randomly contacted by emails or phone calls, when needed, according to their strata (country and if applicable speciality) by the team. Their recruitment will be done as follows:

- HCPs will be invited to participate in the survey (via emails or phone calls). The survey background and objectives, the contact information for questions, and the proposed compensation will be explained to the HCPs at this step. will ensure that the compensation is in line with relevant guidelines of each country and that it only constitutes a compensation for the actual effort and time that is needed to fill-in the questionnaire
- If they agree to participate in the survey, they will click on the link included in the email to access the survey and the instructions for the web questionnaire completion

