- HCPs can also choose to participate in the survey by phone in the local language. In this case, an appointment for a phone interview will be scheduled with them

- HCPs who self-report having treated patients with Alecensa at least once in the 6 months prior to the study and are not employed by a pharmaceutical company,
 , or by regulatory bodies will be eligible to complete the survey. Both parameters are included as screening questions in the questionnaire
- Once HCPs have passed the screening questions of the questionnaire, they are moved through the questions one question at a time. HCPs can only progress to the next question when the previous question was answered. Only wholly completed questionnaires can be submitted
- If the questionnaire is not completed within one week, the HCPs will be sent a reminder by email one week after the link was sent to them
- If the study sample size is not achieved in the stratum (speciality/country), a second reminder by phone will be conducted 1.5 weeks after the link has been sent
- If the questionnaire is still not fully completed, a third and final reminder will be sent to the HCPs by email approximately three weeks after the start of the survey

If necessary, i.e., if the minimum number of needed responders is still not reached, the recruitment will be continued to achieve the study sample size-in a specific stratum.

A HCP will be considered as unreachable if he/she has been contacted between 3 and 5 times without any answer being received.

For each HCP of the sample, the number of contacts, and the date and time when he/she completed the web questionnaire will be recorded. The recruitments in each stratum (HCP speciality/country) will be stopped when the target is reached. If the files have been exhausted in any particular stratum, the recruitments in this stratum will be prematurely ended and a strategy will be determined to adjust the sample size with associated weighting.

The number of HCPs passing the screening questions, incidence rate, and the survey response rate will be monitored regularly by **series**. If the survey response rate or incidence rate is too low, the recruitment may be undertaken in additional countries.

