8.5.2 Sampling Plan

For each selected country, the sample survey will include HCPs identified and recruited from the **selected** list. The **selected** database covers above 90% of the specialities of

interest (i.e., oncologists and pulmonologists) in the target countries (i.e., Austria, Belgium, Germany, Spain, Sweden, and the UK).

A screening question will check whether the physician did ever treat patients with Alecensa in the last 6 months prior to the survey and can therefore be considered for the survey.

With respect to the indication for Alecensa the survey will be deployed amongst oncologists and pulmonologists. The split between the two will depend on who provides care for NSCLC patients in each respective country.

As per sample size defined above and the number of selected countries, the following potential split of sample into strata of the HCPs by country is planned thereby taking into account the size of the country and the HCP universe size (see Table 3)

This table is indicative and will be adjusted according to the final list of countries included and the responsive HCP per strata. It is aimed to have at least 20 completed questionnaires per country.

Planned Country	Overall Number of Completed Questionnairesª	Universe Oncologists ^ь	Universe Pulmonologists ^ь
Germany	50	2900	2400
United Kingdom	45	2700	2500
Spain	45	2300	N/A¢
Austria	20	300	600
Belgium	20	500	700
Sweden	20	600	300
Total	200	N/A	N/A

Table 3 Split of Sample by Country According to a Sample of 200 HCP Questionnaires

^aThe split between specialties depends on the involvement of specialties in the management of advanced lung cancer patients in the different target countries and may be subject to change.

^bUniverse: Numbers of oncologists/pulmonologists in the country according to **according to according (version June** 2018)

^cOnly oncologists are relevant in the treatment of NSCLC in Spain

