8.9 LIMITATIONS OF THE RESEARCH METHOD

Bias

The potential for selection bias of HCPs participating in a survey is an inherent bias/limitation to any study based on volunteer participation.

Among non-response bias, targeted HCPs may also have activated filters in their mail box to block spams and unsolicited emails. They may not even see the invitation to participate in the survey if a very strict degree of message filtering is set. Having multiple email addresses could also be a critical situation. If the one used is not the primary address or if the HCPs do not check their email box frequently they will not receive the invitation during the recruitment period. This is one of the reasons why the HCPs will also be contacted by phone.

Moreover, web surveys may promote social desirability bias which refers to the tendency of physicians to give socially desirable/expected responses instead of choosing those reflecting their current knowledge or clinical practice, e.g., physicians can copy-paste information gathered online instead of giving their own opinions (Wyatt 2000). Social desirability can affect the validity of survey research findings, but the use of prepopulated items in the questionnaire could/tends to reduce this bias (Nederhof 1985).

The access to the web questionnaire interface will be strictly limited to the invited participants, with the possibility to participate only once and a traceability system. Thus, stakeholder bias (multiple answers of people who have a personal interest in survey results and/or who incite peers to fulfil the survey to influence the results) or unverified respondents (when it is not possible to verify who responds) are not applicable.

Limits inherent to surveys

In such surveys, the generalisation and external validity of the results is restricted to HCPs who have an active email address or phone number and are willing (and able) to answer a questionnaire. These HCPs may not be fully representative of the whole targeted HCP population (Wyatt 2000).

Generalisation of the survey results

The raw survey results cannot be generalized to the overall HCP target population, except if a sample adjustment is applied. For more transparency and accuracy, both unweighted (i.e., raw data) and weighted results will be presented in the report.

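### Prescriber status rests on a self-reported screen that comes after product and payment are disclosed, and section 8.9 does not cover misreported eligibility

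*Protocol*

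**What the plan says.** The order of events for an invited HCP is as follows.

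- **Invitation (Protocol 8.4.2).** "The survey background and objectives, the contact information for questions, and the proposed compensation will be explained to the HCPs at this step".
- **Questionnaire introduction (Appendix 2).** It gives the purpose as being to "evaluate the effectiveness of risk minimization measures for Alecensa® (alectinib) in the EU", names the sponsor, and continues: "As appreciation for the time you will dedicate to complete the questionnaire you will be compensated with", with the amount to be adapted to specialty and country.
- **Screening (8.4.2 and 8.5.2).** Eligible are "HCPs who self-report having treated patients with Alecensa at least once in the 6 months prior to the study" who also pass an employment exclusion. "Both parameters are included as screening questions in the questionnaire". Section 8.5.2 describes the use screen as one item: "A screening question will check whether the physician did ever treat patients with Alecensa in the last 6 months prior to the survey".

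The sampling frame in 8.4.1 and 8.5.2 is defined by specialty. Section 8.6.1, although its text is broken, reads as saying that HCPs' answers will not be queried.

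On bias, section 8.9 relies on invitation-only access, single participation and traceability, and concludes that "unverified respondents (when it is not possible to verify who responds) are not applicable".

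**The concern.** The research question in 7.1 is about prescribing HCPs, so use of Alecensa in the last 6 months decides who belongs in the analysis. When the HCP is asked about use, the topic and the compensation are already known. The answer that leads on to the paid questionnaire is then easy to guess. The frame was not built from known users, so it may contain many non-users.

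A non-user who passes enters the denominators of the awareness, knowledge and clinical practice targets (75%, 60% and 75% in 8.7) and answers practice questions without any practice to report. The survey could then miss or meet a target for reasons unrelated to how well the label works among prescribers. Weighting by country and specialty does not correct this, because the error lies within each stratum.

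The controls listed in 8.9 establish who opened the link. They do not establish whether that person has used the product.

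**Working it through.** **1. The plan's own figures.** With P = 0.5 and n = 200 (8.5.1), the half-width is 1.96 × √(0.5 × 0.5 / 200) = 0.0693, which agrees with the stated ±6.9%. Invitations: 200 / 0.10 = 2,000, also as stated. There is no arithmetic error. These figures describe random error only and say nothing about misclassified eligibility.

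**2. The frame (Table 3).** Oncologists: 2,900 + 2,700 + 2,300 + 300 + 500 + 600 = 9,300. Pulmonologists: 2,400 + 2,500 + 600 + 700 + 300 = 6,500. Total: 15,800. The protocol gives no share of these who use Alecensa.

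**3. Share of false passers among completes.** Let E be the share of true users among those who reach the screener, and f the share of non-users who claim use and complete. Assume that all true users who reach the screener complete. Then

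c = (1 − E)f / [E + (1 − E)f].

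E and f are assumptions. Example: E = 10%, f = 5% gives 0.045 / 0.145 = 31%.

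| | E = 10% | E = 20% | E = 30% | E = 50% |
|---|---|---|---|---|
| f = 2% | 15% | 7% | 4% | 2% |
| f = 5% | 31% | 17% | 10% | 5% |
| f = 10% | 47% | 29% | 19% | 9% |

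**4. The same calculation starting from invitations.** Let q be the share of true users among invitees, r their completion rate, and g the share of invited non-users who falsely pass and complete. Then c = (1 − q)g / [qr + (1 − q)g]. With r = 20% and g = 1%, c is 31%, 17%, 10% and 5% at q = 10%, 20%, 30% and 50%. This repeats the f = 5% row because g/r = 5%. With g = 0.5%, c is 18%, 9%, 6% and 2%.

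**5. Effect on the knowledge target (60%).** Assume true users reach a level of 65% and false passers 45%. The pooled level is 65 − 20c.

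| | E = 10% | E = 20% | E = 30% | E = 50% |
|---|---|---|---|---|
| f = 2% | 61.9% | 63.5% | 64.1% | 64.6% |
| f = 5% | 58.8% | 61.7% | 62.9% | 64.0% |
| f = 10% | 55.5% | 59.3% | 61.2% | 63.2% |

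The target is missed when 20c exceeds 5, that is, when c exceeds 25%. In this grid that happens at E = 10% with f = 5% or 10%, and at E = 20% with f = 10%.

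**6. Effect on a 75% target.** Assume true users are at 80% and false passers 30 points lower. The exact binomial chance that at least 150 of 200 unweighted completes meet the criterion is 0.97 with c = 0. It is 0.78 with c = 10% (pooled 80 − 3 = 77%) and 0.41 with c = 20% (pooled 80 − 6 = 74%).

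**7. Compared with the stated precision.** The bias is c times the score gap. It exceeds 6.9 points when c is above 6.9/40 = 17% for a 40-point gap, or 6.9/20 = 35% for a 20-point gap. Steps 5 and 6 assume that false passers score lower. If they look up or guess the expected answers, which 8.9 concedes respondents can do, the gap can shrink or change sign.

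**The case against.** Several points on the other side stand.

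- **Section 8.9.** A reader might infer that 8.9 is wrong to dismiss unverified respondents. The protocol defines that term by whether one can tell who responds, and invitation-only, traceable access is a relevant control for that. The section is silent on misreported use; it is not mistaken on its own definition.
- **Invitation and screener wording.** Neither text could be read here. That the invitation names Alecensa is a strong inference from its having to explain the objectives, not a stated fact. Decoy products in the screener cannot be excluded, although they would help little once the introduction has named the product.
- **Detection.** A reader might infer that nothing in the plan could reveal the problem. Section 8.4.2 has the number passing the screen, the incidence rate and the response rate monitored, so an implausibly high pass rate could be noticed. Section 8.3 collects the number of Alecensa patients treated, and 8.7 allows that number to be used in describing HCPs with incorrect answers. These are partial safeguards: the count is itself self-reported, the 8.7 description is optional, and neither is tied to checking eligibility.
- **Incentive.** Payment covers time and effort only, and a false passer must finish about 15 minutes of mandatory items as a traceable invitee. Announcing the topic may also deter non-users from opening the link, which would raise E.
- **Stating compensation beforehand.** This is not a defect. The charter cited in 9.1.3 requires it, and 9.1.1 requires HCPs to be informed of the purpose.

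What remains is that population membership depends on one unverified answer given after the topic and the payment are known.

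**Conclusion.** The concern holds as a weakness of design and of the stated limitations. Some non-users could pass the screen and be analysed as prescribers, and 8.9 does not mention it. Section 8.4.2 says openly that use is self-reported, so the protocol does not contradict itself on this point.

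Under assumed eligible shares of 10% to 50% and a 5% false-claim rate, false passers would be about 31% down to 5% of completes. Every input to that range is assumed.

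A reader might go further and infer that the results will be contaminated or that a target will be wrongly missed. The protocol does not support that. It gives neither an eligible share nor a false-claim rate, the 60% target is missed only in the more extreme scenarios shown, and the direction of the bias is unknown. The change is worth making because it is cheap before fieldwork, whereas false passers could not be reliably identified afterwards.

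**What to change.** 1. **Invitation.** Describe the survey in general terms, as being about the safety of lung cancer medicines, with the compensation still stated.
2. **Screener first.** Ask which of several listed products the HCP has prescribed in the last 6 months, with Alecensa as one of them.
3. **Full disclosure next.** Show the Alecensa-specific introduction, the sponsor, the full purpose and the consent immediately after the screener and before any survey item. Discard the screening answers of those who do not pass or do not consent.
4. **Section 8.9.** State that eligibility is self-reported and may be misclassified, separately from the sentence on respondent identity.
5. **Analysis.** Use the number of Alecensa patients treated for a sensitivity analysis of the three targets that excludes zero or implausible reports.

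The cost is a reworded invitation, one changed screening question, a moved introduction, a sentence in 8.9 and one extra analysis of data already collected. The downside is that product and sponsor are disclosed slightly later, which must be compatible with local consent and data-protection rules.
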